1.2 Benefits and Risks for the Study Population

The risks and benefits of hemodialysis are well characterized. The same risks and benefits will apply to patients undergoing dialysis with Theranova dialyzers. During dialysis, toxins and beneficial molecules can be removed. Theranova dialyzers can remove a larger size range of molecules, therefore patients may see greater removal of “middle molecules”, including coagulation factors. Studying these molecules *in vivo* is expected to complement previous *in vitro* investigations on single (simulated) treatment removal of coagulation factors by providing longer term data.

Studies of therapies that remove middle molecules more effectively than HD with typical high permeability dialyzers do not suggest that there is an increased risk from removing solutes of this size, and indicate that there may be benefits to removal of the uremic

toxins. The recent progress in dialysis treatment may improve the removal of these toxins and though there is insufficient evidence on reducing mortality there may be benefits on patient outcomes.¹²

Although the Theranova dialyzer is known to remove more albumin per treatment than high-flux dialyzers, the albumin sieving of the membrane is <1%, which is below what is given by Ward as definition of protein-leaking membranes (1-3%). The average clinical albumin loss of 3 g per 4 h hemodialysis session¹⁶ is also at the lower end of his definition (2-6 g/4 h). Increased patient mortality is correlated with low serum albumin levels, but not directly correlated with albumin loss per treatment. Human serum albumin homeostasis in general and in various disease states¹⁷, particularly in patients on dialysis, has been extensively reviewed. Although observational studies have shown a significant association between lower serum albumin level and greater risk of all-cause death, in HD patients as well as in peritoneal dialysis (PD) patients recent research has led to the conclusion that the association between serum albumin and outcome is principally mediated by inflammation and that, at least in renal failure patients, there is evidence that plasma concentration is determined primarily by the rate of liver albumin synthesis, and this synthesis is decreased in inflammatory states. Albumin is a negative acute phase reactant and uremic inflammation, which is common in dialysis patients, is a main determinant of a low serum albumin level through reduced synthesis of albumin.^{18,19} Inflammation is in itself a significant and powerful risk factor for poor outcome in dialysis patients.²⁰

2. STUDY OBJECTIVES

2.1 Primary Objective(s)

The primary efficacy objective of this study is to demonstrate that the Theranova 400 dialyzer has performance superiority to the Elisio-17H dialyzer in removing lambda immunoglobulin free light chains (λ FLCs).

The primary safety objective of this study is to demonstrate that performance of the Theranova 400 dialyzer compared to the Elisio-17H dialyzer is non-inferior, in regards to maintaining pre-dialysis serum albumin.

2.2 Secondary Objective(s)

The secondary objectives of this study are to evaluate the performance of the Theranova 400 dialyzer compared to the Elisio-17H dialyzer in removing serum middle molecules, dialysis adequacy, levels of coagulation factors, and characterize monthly trends in pre-dialysis serum albumin levels.

2.3 Exploratory Objectives

The exploratory objectives for this study include:

- Evaluation of patient reported quality-of-life assessments.
- Evaluation of serum levels of the inflammatory marker high sensitivity C-Reactive Protein.

3. INVESTIGATIONAL PLAN

[figure not shown]
3.1 Overall Study Design and Plan

This is a multi-center, prospective, randomized, controlled, open-label, parallel study to evaluate medically stable ESRD patients receiving dialysis treatment with either the Theranova 400 dialyzer or the Elisio-17H dialyzer for 3 sessions weekly, over 24 weeks.

A sufficient number of patients will be enrolled in the study in order to randomize 166 patients in a 1:1 manner to either the Theranova 400 dialyzer or the Elisio-17H dialyzer. The study will be conducted in up to 30 study centers in the USA.

The study will have an overall duration of approximately 27 weeks per patient. This period will consist of up to 2 weeks screening period, followed by a first treatment day visit and consequent 3 dialysis sessions per week in an in-center setting over a 24 week period, at the end of the study there will be a visit occurring on the next HD session. The assessments performed, on a monthly basis, are shown in the Schedules of Evaluation in [Appendix 1](#) and [Appendix 2](#). Patients will initiate their HD treatment on their randomized study dialyzer, either Theranova 400 dialyzer or Elisio-17H dialyzer, at the midweek HD session (Wednesday or Thursday), and will then continue to have 3 dialysis sessions per week. During the treatment period, initial blood samples will be taken on the day of the first study dialyzer treatment and subsequent blood sampling samples will be taken after each 4 weeks of treatment, during the midweek HD session as illustrated in [Appendix 1](#). A scheme for the study is shown in [Figure 1](#) below. The overall duration of the complete study will be approximately 9 months to allow sufficient time for patient recruitment.

Figure 1. Trial Schematic^a

^a All study visits are performed during the mid-week treatment session.

3.2 Study Endpoints

3.2.1 Primary Endpoints

The primary efficacy endpoint is the Reduction Ratio (RR) of λ FLC after 24 weeks of treatment.

The primary safety endpoint is the pre-dialysis serum level of albumin after 24 weeks of treatment.

3.2.2 Secondary Endpoints

Secondary efficacy endpoints include:

- Reduction ratio of λ FLC measured on the first day of treatment and after 4 weeks of treatment.
- Reduction ratio of complement factor D (CFD; MW = 27 kDa), κ FLC (MW = 23 kDa), interleukin 6 (IL-6; MW = 25 kDa), tumor necrosis factor alpha (TNF α ; MW = 51 kDa), and β_2 -microglobulin (MW = 11.6 kDa) measured after 4 weeks and after 24 weeks of treatment.
- Change in pre-dialysis β_2 -microglobulin measured on the first day of treatment and after 24 weeks of treatment.
- Kt/V_{urea} measured after every 4 weeks of treatment.

Secondary safety endpoints include:

- Pre-dialysis serum albumin measured on the first day of treatment and after every 4 weeks of treatment.
- Pre-dialysis Factor VII (MW = 50 kDa), Protein C (MW = 53-62 kDa) and Factor II (MW = 72 kDa) measured on the first day of treatment, after 4 weeks and after 24 weeks of treatment.
- Pre-dialysis Vitamin A measured on the first day of treatment, after 4 weeks and after 24 weeks of treatment.
- nPNA (nPCR) calculated after every 4 weeks of treatment.
- Change from baseline to final measure in chemistry and hematology laboratory tests (see [Table 1](#)).
- Monitoring of adverse events (AEs), serious adverse events (SAEs) and product complaints (PCs) for Baxter related devices.

3.2.3 Exploratory Assessments

Exploratory assessments include:

- Inflammatory marker high-sensitivity C-Reactive protein (hs-CRP) measured pre-dialysis on the first day of treatment and after every 4 weeks of treatment.
- KDQOL-36 measured on the first day of treatment, after 12 weeks and after 24 weeks of treatment.
- EQ-5D-5L measured on the first day of treatment, after 12 weeks and after 24 weeks of treatment.
- Changes in utilization for medication (i.e., erythropoiesis-stimulating agent (ESA), anti-hypertensives, iron).

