5.5 Blinding

This is an open-label study and will not have blinding of any investigational products. However, the Medical Monitor, Study Statistician, Data Management and the central laboratory will be blinded to treatment as a means to minimize potential bias. A non-blinded statistician will be assigned to this study.

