10.7 Exploratory Endpoints

An MMRM model will be used to evaluate differences between treatment groups in the change from baseline in pre-dialysis serum levels of hs-CRP after each 4 weeks of treatment. The model will include the fixed effect of treatment, visit, as well as the continuous, fixed covariate of baseline measurement and the random effect of patient.

An MMRM model will be used to evaluate differences between treatment groups in the change from first day of treatment in KDQOL-36 and EQ-5D-5L after 12 weeks and after 24 weeks of treatment. The model will include the fixed effect of treatment, visit, as well as the continuous, fixed covariate of screening measurement and the random effect of patient.

Appropriate models will be used to evaluate differences between treatment groups in the utilization for medications (i.e., ESA, anti-hypertensives, iron).

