Appendix 1 Schedule of Evaluations and Procedures

Evaluation	Screening Visit Days - 14 to - 1	Treatment Period														End of Study Visit	
		Visit 1 1 st Treatment Day		Visit 2 Week 4		Visit 3 Week 8		Visit 4 Week 12		Visit 5 Week 16		Visit 6 Week 20		Visit 7 Week 24			
		Pre-dialysis	Post-dialysis	Pre-dialysis	Post-dialysis	Pre-dialysis	Post-dialysis	Pre-dialysis	Post-dialysis	Pre-dialysis	Post-dialysis	Pre-dialysis	Post-dialysis	Pre-dialysis	Post-dialysis		
Informed consent	X																
Demographics	X																
Medical histories (past and present)	X																
Physical examination including weight ^a	X															X	
Vital Signs	X	X	X	X	X	X	X	X	X	X	X	X	X	X	X	X	
Randomization ^b	X																
AE/SAE/ADE/PC ^c	X	X	X	X	X	X	X	X	X	X	X	X	X	X	X	X	
Concomitant medications ^d	X	X	X	X	X	X	X	X	X	X	X	X	X	X	X	X	
HD prescription and Ultrafiltration ^e	X		X		X		X		X		X		X		X		
Body weight	X	X	X	X	X	X	X	X	X	X	X	X	X	X	X	X	
Laboratory Evaluations ^f	X	X		X	X	X	X	X	X	X	X	X	X	X	X	X	
Patient Reported outcomes ^g			X						X						X		

Note: All sampling visits will be performed during the mid-week treatment

^a Weight will be measured at screening and end of study, height will be measured only at screening

^b Eligible patients will be randomized at the end of the Screening Period

^c AEs, SAEs and PCs will be collected after the informed consent is signed and throughout the study, until the end of study visit ADEs will be collected throughout the treatment period

^d Medications will be collected throughout the study

^e Ultrafiltration (UF) will be obtained at the end of treatment of each 4 week treatment period

^f Collection of laboratory samples is presented in the Schedule of Clinical Laboratory Evaluations below

^g Patient reported outcomes (PROs) will include KDQOL-36 and EQ-5D-5L. All PROs will initially be assessed during the first treatment day, after 12 weeks of treatment and at the end of the study, following 24 weeks of treatment

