5.5 Schedule of Visits and Procedures

All clinical study evaluations will be performed according to the listed below. If a patient discontinues from the study prematurely, every attempt will be made to perform all of the procedures and evaluations that are scheduled for the final visit (i.e. end of study visit).

| | | Treatment Period | | | | | | | | | | | | | | |
|--|----------------------------------|-----------------------------------|-------------------|-------------------|-------------------|-------------------|-------------------|--------------------|-------------------|--------------------|-------------------|--------------------|-------------------|--------------------|-------------------|--------------------------|
| | Screen ing Visit Days - | Visit 1 1 st Treatn | ient Day | Visit 2 Week 4 | | Visit 3 Week 8 | | Visit 4 Week 12 | | Visit 5 Week 16 | | Visit 6 Week 20 | | Visit 7 Week 24 | | End of Study Visit |
| Evaluation | 14 to - 1 | Pre- dialysis | Post- dialysis | Pre- dialysis | Post- dialysis | Pre- dialysis | Post- dialysis | Pre- dialysis | Post- dialysis | Pre- dialysis | Post- dialysis | Pre- dialysis | Post- dialysis | Pre- dialysis | Post- dialysis | |
| Informed consent | Х | | | | | | | | | | | | | | | |
| Demographics | Х | | | | | | | | | | | | | | | |
| Medical histories (past and present) | х | | | | | | | | | | | | | | | |
| Physical examination including weight ^a | Х | | | | | | | | | | | | | | | х |
| Vital Signs | Х | Х | Х | Х | Х | Х | Х | Х | Х | Х | Х | Х | Х | Х | Х | Х |
| Randomization ^b | Х | | | | | | | | | | | | | | | |
| AE/SAE/ADE/PC° | Х | Х | Х | Х | Х | Х | Х | Х | Х | Х | Х | Х | Х | Х | Х | Х |
| Concomitant medications ^d | Х | х | х | х | x | х | х | x | х | х | х | x | х | х | х | х |
| HD prescription and Ultrafiltration ^e | x | | х | | x | | х | | х | | х | | Х | | х | |
| Body weight | Х | Х | Х | Х | Х | Х | Х | Х | Х | Х | Х | Х | Х | Х | Х | Х |
| Laboratory Evaluations ^f | Х | Х | | Х | Х | Х | Х | Х | Х | Х | Х | Х | Х | Х | Х | Х |
| Patient Reported outcomes ^g | | | Х | | | | | | Х | | | | | | Х | |

Table 1. Schedule of Visits and Procedures

Note: All sampling visits will be performed during the mid-week treatment.

^a Weight will be measured at screening and end of study, height will be measured only at screening.

^b Eligible patients will be randomized at the end of the Screening Period.

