13. EXPLORATORY ANALYSES

An MMRM model will be used to evaluate differences between treatment groups in the change from baseline in pre-dialysis serum levels of hs-CRP after each 4 weeks of treatment. The model will include the fixed effect of treatment, visit, as well as the continuous, fixed covariate of baseline measurement and the random effect of patient.

An MMRM model will be used to evaluate differences between treatment groups in the change from first day of treatment in KDQOL-36 and EQ-5D-5L after 12 weeks and after 24 weeks of treatment. The model will include the fixed effect of treatment, visit, as well as the continuous, fixed covariate of screening measurement and the random effect of patient.

Cumulative doses in the utilization for medications (i.e., ESA, anti-hypertensive, iron and phosphate) over 4 weeks intervals across 24 weeks study treatment will be summarized descriptively. An MMRM model will be used to evaluate differences between treatment groups in the change from accumulation of 4 weeks prior to study treatment after 4, 8, 12, 16, 20 and 24 weeks study treatment. The analysis of the exploratory endpoints will be carried out on the FAS.

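### The first KDQOL-36 and EQ-5D-5L are scheduled after the first open-label study session, so the change analysis has no pre-exposure reference (low severity)

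*Protocol*

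**What the plan says.** The timing is fixed by the visit schedules and not by the endpoint text.

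- **Endpoint text.** Protocol 3.2.3 has "KDQOL-36 measured on the first day of treatment, after 12 weeks and after 24 weeks of treatment", with the same days for EQ-5D-5L. Protocol 8.5.1 lists the questionnaires among the visit-day data, again without a time within the session.
- **Schedules.** Protocol Appendix 1 and the row "Patient Reported outcomes" in SAP Table 1 each carry three marks, all post-dialysis: Visit 1, Visit 4 (Week 12) and Visit 7 (Week 24). Neither has a mark at screening or at Visit 1 pre-dialysis. A footnote confirms that nothing comes earlier: "All PROs will initially be assessed during the first treatment day, after 12 weeks of treatment and at the end of the study".
- **Order of events.** "Eligible patients will be randomized at the end of the Screening Period". Protocol 3.1 adds: "Patients will initiate their HD treatment on their randomized study dialyzer". Protocol 5.5 states: "This is an open-label study and will not have blinding of any investigational products". Patients are not among the parties it keeps blinded.
- **Analysis.** SAP 13, like Protocol 10.7, models "change from first day of treatment in KDQOL-36 and EQ-5D-5L after 12 weeks and after 24 weeks of treatment". Both name a "fixed covariate of screening measurement and the random effect of patient".

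**The concern.** A change score needs a reference that treatment cannot have influenced. Here the reference is recorded when the patient has completed one session on the assigned dialyzer, in a trial where nothing hides the assignment. If the arms already differ at that point, through the device or through expectation, the difference sits in the reference and is taken out of the later comparison. An early difference with the same sign as the later one pulls the result toward zero; one with the opposite sign inflates it.

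The analysis as planned cannot recover from this. The pre-dialysis baseline definitions (Protocol 10.1, SAP 5.2) cover laboratory values and, in the SAP, vital signs, but not questionnaires. At stake is the interpretation of the quality-of-life results, an exploratory objective.

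**Working it through.** The documents give no effect size, SD or power for the questionnaires, so there is no stated figure to reproduce.

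**1. Reading the schedules.** The questionnaire row of each table was set cell by cell against its header: label, screening, pre and post for Visits 1 to 7, end of study. Both rows give Visit 1 post, Visit 4 post and Visit 7 post. Two other rows confirm the alignment. The prescription and ultrafiltration row falls at screening and then only in post-dialysis columns, which agrees with its footnote. The laboratory row has Visit 1 pre-dialysis only, which agrees with Protocol Appendix 2. The screening procedures in Protocol 8.4.1 include no questionnaire.

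**2. What the change score estimates.** Let D24 be the true between-arm difference at Week 24, D0 the difference already present in the Visit 1 post-session value, and b the within-arm slope of the Week 24 value on the Visit 1 value.

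- Change without a covariate: D24 − D0.
- Change adjusted for the Visit 1 value: D24 − b × D0.
- Change adjusted for a pre-randomization screening value, if one existed: still D24 − D0 in expectation, because randomization balances that covariate between arms while D0 stays in the reference.

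The first two formulas were checked with assumed inputs D24 = 0.30 SD, D0 = 0.20 SD, b = 0.6. Expected: 0.30 − 0.20 = 0.10 and 0.30 − 0.6 × 0.20 = 0.18. A simulation of 400,000 patients gave 0.100 and 0.180. These inputs test the algebra only; they are not an estimate of the size.

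**3. Size.** Write D0 = f × D24. The proportional loss is f without adjustment and b × f with adjustment for Visit 1.

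- *Even accrual (assumed).* Protocol 5.8 expects 73 treatments. At Week 24, f = 1/73 = 1.4%. With b from 0.3 to 0.7 (assumed), the adjusted loss is 0.3 × 1.4% = 0.4% to 0.7 × 1.4% = 1.0%. At Week 12 the session number is 3 × 12 + 1 = 37, so f = 1/37 = 2.7%.
- *Fully immediate effect (assumed).* f = 1: the unadjusted change shows nothing, and the adjusted change keeps a fraction 1 − b.

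The documents do not say where between these ends f lies. If both arms shift equally after the session, D0 = 0 and nothing is lost.

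**4. What each timing of the reference removes.**

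| Reference value | Session exposure | Knowledge of allocation |
|---|---|---|
| Visit 1 post-dialysis (as planned) | remains | can remain |
| Visit 1 pre-dialysis | removed | can remain |
| Screening, before randomization | removed | removed |

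**The case against.** The case for leaving the schedule alone has real weight.

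- One session is a small exposure. Entrants have had at least 3 months of high-flux dialysis (Protocol 4.2), and Protocol 3.3 describes the comparator as similar in design, surface area and performance. The difference between arms after a single session may well be close to nothing. This stands, and it is why no large loss is claimed.
- All three questionnaires are taken under the same post-dialysis condition, so each patient's change is like for like, and fatigue common to both arms cancels. This also stands. It means that moving only the first questionnaire would be a mistake.
- In an open-label trial an early expectation effect is not device benefit, so subtracting it is not plainly a loss. That is fair for the expectation part, but it does not cover an early device effect, and the two cannot be separated from the planned data.
- The endpoints are exploratory, outside both testing hierarchies, and carry no power claim. This sets the priority but does not remove the point.

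A reader might also infer that the sponsor breaks its own rule, on the ground that every laboratory baseline is pre-dialysis on the first treatment day. The documents do not support that: BUN, liver function and coagulation have no Visit 1 sample, and SAP 11.3 measures BUN change from screening.

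**Conclusion.** The concern holds at low severity. Both schedules place the reference questionnaire after a full open-label session on the randomized dialyzer, no earlier value is collected, and the covariate named in the model is not scheduled. The mechanism follows from the plan's text; the size does not. It is about 1.4% of the Week 24 effect if benefit accrues evenly over 73 sessions, and larger only to the extent that the arms separate at once.

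Two stronger readings are tempting. One is that a substantial share of the quality-of-life effect is lost; that needs a large immediate between-arm effect, which the documents neither report nor assume. The other is that the trial's main conclusions are at risk. They are not: the primary and secondary endpoints do not use these data.

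**What to change.** In Protocol Appendix 1 and SAP Table 1, move the questionnaire marks from the post-dialysis to the pre-dialysis column at Visits 1, 4 and 7 together. State in Protocol 3.2.3 and SAP 13 that the Visit 1 questionnaires are completed before the first study session, and define that value as the questionnaire baseline. This removes the exposure component only.

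To remove expectation from known allocation as well, have the first questionnaire completed at the existing screening visit before randomization. That also supplies the screening covariate already named in the model. Change must then be measured from the screening value; using it only as a covariate while still subtracting Visit 1 would leave the problem in place. Whichever option is chosen, Protocol 10.7 and SAP 13 should name a covariate that the schedule collects.

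The cost is a protocol amendment and a move within visits that already exist, on the same ePRO device. The screening option means that some patients who are never randomized also fill in the forms. The real downside is a mixed reference: patients already enrolled have a post-session first value. Flag them and repeat the questionnaire analysis without them, or keep their follow-up questionnaires post-dialysis so that their own change stays like for like. For these patients, a supplementary comparison of the Week 12 and Week 24 values themselves, without subtracting Visit 1, avoids the reference problem by randomization, at some cost in precision.

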3.3 Rationale for Study Design and Control Group

This multi-center, prospective, randomized, controlled, open-label, parallel study is designed to demonstrate superiority of the Theranova 400 dialyzer compared to the Elisio-17H dialyzer in regards to removal of λ FLCs and safety of the Theranova 400 dialyzer during extended use (study duration 24 weeks). The Elisio-17H dialyzer is a marketed, Food and Drug Administration (FDA) cleared hemodialyzer device with comparable design, membrane polymers and surface area, and performance specifications to the study device. The main difference between the Theranova 400 dialyzer and the Elisio-17H dialyzer is the larger pore size within the Theranova 400 dialyzer, which allows a wider range of molecules to diffuse across the device membrane without the need of convection.

Both devices will be studied in medically stable patients who require chronic hemodialysis therapy due to end stage renal disease. The dialysis prescriptions for the Theranova 400 dialyzer follow the same method as for a conventional high-flux dialyzer; no device-specific modifications to the dialysis prescriptions are required. Use of the study devices during the study treatment period is consistent with conventional, current institutional practice.²¹

Benefits of the Theranova dialyzer products are associated with the removal of serum middle molecules. The removal of serum middle molecules such as λ FLCs, may be associated with a reduction in both patient morbidity and mortality.²²⁻²⁵ Data from this clinical study will also be used to support the new device classification for Theranova dialyzer, as a new device modality that effectively reduces serum levels of middle molecules such as λ FLCs during individual HD treatments.

As part of this evaluation, Baxter has chosen to study representative beneficial molecules in addition to uremic toxins. Baxter has selected three beneficial molecules to study. The pre-dialysis serum levels of the following molecules will be measured on the first day of treatment, after 4 and after 24 weeks of treatment:

1. Factor VII (Activates IX, X): 50,000 Da (bleeding diathesis)
2. Protein C: 53,000-62,000 Da (deficiency causes hypercoagulable state)
3. Factor II: 72,000 Da (deficiency causes bleeding disorder)

In addition, Vitamin A levels will be measured on the first day of treatment, after 4 weeks and after 24 weeks of treatment.

We have focused on coagulation factors because coagulation abnormalities such as hypercoagulability and thrombosis are common in patients with end stage renal disease on maintenance hemodialysis. The selected molecules have deficiencies that manifest phenotypically, are well described (Factor VII deficiency, Factor II deficiency, Protein C deficiency), and represent different parts of the coagulation cascade. They are too large to be effectively removed by high-flux hemodialysis only, but represent the higher end of the Theranova dialyzer removal range. Studying these molecules *in vivo* is also expected to complement previous *in vitro* investigations on single (simulated) treatment removal of coagulation factors by providing longer term data for potential changes in coagulation factors. Baxter believes that the comparison of the Theranova dialyzer cohort to the high-flux dialysis control group will examine the significance of changes in serum levels.

